10.1 Prior Medication

Prior medication is defined as any medication with a start and stop date prior to the date of the first dose of open-label pimavanserin. Summaries of prior medications will be provided for the Open-label Safety Analysis Set and Double-blind Safety Analysis Set.

10.2 Concomitant Medication

10.2.1 Analysis for the Open-label Period

Concomitant medication during the open-label period is defined as any medication with a start date prior to the date of first dose of open-label pimavanserin and continuing after the date of first dose of open-label pimavanserin or with a start date between the date of the first dose of open-label pimavanserin and before the date of the first dose of double-blind study drug for subjects randomized into the double-blind period or last dose in the open-label period for subjects not randomized, inclusive. Concomitant medications during the open-label period will be summarized for the Open-label Safety Analysis Set.

10.2.2 Analysis for the Double-Blind Period

Concomitant medication during the double-blind period is defined as any medication with a start date prior to the date of first dose of double-blind study drug and continuing after the date of first dose of double-blind study drug or with a start date between the dates of the first and last doses of double-blind study drug, inclusive. Concomitant medications during the double-blind period will be summarized for the Double-blind Safety Analysis Set.

10.3 Analysis for Post-Treatment Medication

Post-treatment medication is defined as any medication with a start date after the date of the last dose of open-label pimavanserin for non-randomized subjects and after the date of the last dose of double-blind study drug for randomized subjects. Summaries of post-treatment medications will be provided for the Open-label Safety Analysis Set.

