1.3.1 Parkinson's Disease Psychosis Program

The scope of the development program for pimavanserin is the largest ever conducted in PDP. At the time of approval, 616 mostly older, late-stage PDP subjects had been evaluated in 16 countries over a span of >10 years. Clinically meaningful efficacy was established in Study ACP-103-020, a 6-week, placebo-controlled Phase 3 study (Cummings et al. 2014). This efficacy was supported by data from additional short-term Phase 2b/3 studies. In ACP-103-020, pimavanserin 34 mg consistently demonstrated statistically significant efficacy across multiple and independent endpoints, subject subgroups, and sensitivity analyses. Improvements in sleep and daytime wakefulness were also observed. These clinical

benefits were achieved without worsening of Parkinson's disease motor symptoms and without a number of other safety concerns associated with atypical antipsychotics.

Pimavanserin is considered to be generally safe and well tolerated. Across all clinical studies of pimavanserin, the most frequently reported treatment-emergent adverse events (TEAEs) were in the central nervous system (CNS), gastrointestinal, and psychiatric systems. Most events were mild to moderate in intensity. The most common CNS TEAEs included dizziness (including postural), headache, and somnolence (drowsiness). Common gastrointestinal disturbances included dyspepsia, nausea, constipation, and vomiting. Severe nausea and vomiting were dose limiting in a few cases. Reported psychiatric conditions included agitation, insomnia, and confusional state.

Clinical and nonclinical safety pharmacology studies of pimavanserin suggest a potential risk for QT prolongation. The magnitude of effect in humans has been assessed in a thorough QT study with doses of pimavanserin ranging from 17 to 68 mg. In the Phase 3 PDP program, an average prolongation of approximately 5 to 8 ms was observed with pimavanserin 34 mg.

The US package insert for pimavanserin has a boxed warning that elderly patients with dementia-related psychosis treated with antipsychotic drugs are at an increased risk of death. Pimavanserin is not approved in the treatment of patients with dementia-related psychosis unrelated to the hallucinations and delusions associated with Parkinson's disease psychosis.

Additional information is provided in the pimavanserin Investigator's brochure and in the NUPLAZID[®] (pimavanserin) US package insert.

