4.5 Prior and Concomitant Therapy

Lifetime antipsychotic use and response is to be recorded. All other medications used up to 24 weeks prior to Visit 2 through Visit 18 (telephone visit) or ET are to be recorded.

In order to ensure that appropriate concomitant therapy is administered, it is essential that subjects be instructed not to take any medication without prior consultation with the Investigator (unless the subject is receiving treatment for a medical emergency).

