6.3.8 Safety Follow-up

A 4-week safety follow-up telephone contact is to be completed for all subjects. Subjects will have the following completed via telephone approximately 4 weeks after the last dose of study drug:

- Assessment of concomitant medications/treatments
- Assessment of AEs

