5.1.1 Open-label Period

In general, dates associated with open-label data will be accompanied on the listings by the study day relative to the date of first dose of open-label pimavanserin. Open-label study day 1 is the date of first dose of open-label pimavanserin.

For assessments occurring on or after the open-label study day 1, open-label study day is calculated for a given subject as

$$\text{assessment date} - \text{first open-label dose date} + 1.$$

For assessments occurring prior to the open-label study day 1, open-label study day is calculated for a given subject as

$$\text{assessment date} - \text{first open-label dose date}.$$

Unless specified otherwise, the following summaries will be provided:

1. all subjects combined;
2. by randomization status (not randomized and randomized);
3. by final dose level (20 and 34 mg) of open-label pimavanserin administered during the open-label period.

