14.1 Adverse Events

All Adverse events (AEs) will be coded using MedDRA version 20.0 or newer.

An AE (classified by preferred term) will be considered a treatment emergent AE (TEAE) if the onset date was on or after the date of first dose of open-label pimavanserin and up to 30 days past the last dose of study drug. AEs reported on Day 1 based on open-label Baseline (pre-dose) findings (e.g. clinically significantly abnormal vital signs, laboratory test results, or electrocardiogram parameters) will not be considered as TEAEs.

Each TEAE will be assigned to either the open-label or double-blind period based on the onset date. For randomized subjects, if the onset date was on or after the date of first dose of double-blind study drug, the TEAE will be assigned to the double-blind period. All other TEAE will be assigned to the open label period.

The event counts and the number and percentage of subjects reporting TEAEs will be tabulated by SOC and preferred term; and, by SOC, preferred term, and maximum severity. If more than 1 AE occurs with the same preferred term for the same subject, the subject will be counted only once for that preferred term using the most severe occurrence for the

summarization by severity. In addition, the event counts and the number and percentage of subjects with TEAEs classified by the Investigators as related to the study drug, with most frequently reported TEAEs (preferred terms reported by $\geq 5\%$ of subjects overall for the open-label period and $\geq 5\%$ of subjects in either treatment group for the double-blind treatment period), with treatment emergent serious AEs, with fatal AEs (i.e. events that cause death), and with TEAEs leading to discontinuation of study drug will be summarized by SOC and preferred term. The display in these tables will be sorted alphabetically by SOC and then by descending subject frequency for the preferred terms using combined counts from both groups within each SOC. The event counts and the number and percentage of subjects with any TEAEs will also be tabulated by preferred term without SOCs. This table will be sorted by descending subject frequency using combined counts from all subjects.

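### Medications started after the last dose are not summarized by treatment arm, although double-blind adverse events are counted by arm for 30 days after that dose

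*SAP*

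**What the plan says.** **Medications.** For randomized subjects, SAP 10.3 defines a post-treatment medication as one started "after the date of the last dose of double-blind study drug for randomized subjects". It then says that "Summaries of post-treatment medications will be provided for the Open-label Safety Analysis Set". SAP 5.1.1 gives three default displays for open-label summaries: all subjects, randomized versus not randomized, and final open-label dose. None is by double-blind arm. The neighbouring categories are treated differently. Prior medications (SAP 10.1) are summarized for both safety sets. Double-blind concomitant medications (SAP 10.2.2) are summarized for the Double-blind Safety Analysis Set, but cover only drugs already in use at the first double-blind dose or "with a start date between the dates of the first and last doses of double-blind study drug, inclusive".

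**Adverse events.** Under SAP 14.1 the treatment-emergent window runs "up to 30 days past the last dose of study drug". In randomized subjects, every such event from the first double-blind dose onward belongs to the double-blind period, and SAP 14 displays that period by treatment group. No table described in the SAP separates onset before and after the last dose, or before and after the start of another antipsychotic.

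**Conduct.** Under Protocol 3.4 a subject who relapses is taken off study drug and enters safety follow-up, which lasts about 4 weeks. Under Protocol 4.5.1 the medication prohibitions apply up to Visit 17/ET. Protocol 4.5 says that medications used "through Visit 18 (telephone visit) or ET are to be recorded". Protocol 6.3.8 lists "Assessment of concomitant medications/treatments" at the 4-week call for all subjects.

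**The concern.** The 30-day window overlaps the period in which a relapsed subject may first receive another antipsychotic. An adverse event that begins on that drug is then counted under pimavanserin or placebo. The safety objective is the comparison of those two columns, and the drug is meant to make relapse less frequent in one of them, so the contribution of rescue-period events may differ by arm. A reader would need post-treatment antipsychotic use by arm to judge this, and that is the one medication category without a by-arm summary. If the split is not prespecified, any later attempt to separate these events will be made after unblinding.

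The recording rule adds a second difficulty. If a site reads Protocol 4.5 as ending medication recording at ET, the data for early terminators could be missing even though Protocol 6.3.8 expects them.

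**Working it through.** **Inputs** (Protocol 9.3, SAP 3.4): relapse over 26 weeks of 60% on placebo and 35% on pimavanserin; dropout 25%; 75 events; 89 subjects per arm. Exponential times are assumed, with dropout competing with relapse.

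**1. The plan's own figures.**
- Cumulative hazards over 26 weeks: placebo −ln(0.40) = 0.916; pimavanserin −ln(0.65) = 0.431; dropout −ln(0.75) = 0.288. Hazard ratio = 0.431/0.916 = 0.470, as stated.
- Schoenfeld events for a fixed design: 4 × (1.960 + 1.282)² / (ln 0.470)² = 73.8. With the O'Brien-Fleming boundary at 38 of 75 events, power is 0.899 for 74 events and 0.903 for 75. The stated 75 is reproduced.
- Observed relapse probability = λ/(λ + δ) × (1 − exp(−(λ + δ))), with λ the relapse and δ the dropout hazard. Placebo: 0.916/1.204 × 0.700 = 0.533. Pimavanserin: 0.431/0.719 × 0.5125 = 0.307.
- Sample size = 75/0.420 = 178.6, against 178 stated.

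**2. Relapsers entering the window.** Placebo 89 × 0.533 = 47.4; pimavanserin 89 × 0.307 = 27.3; total 74.8. Placebo share = 47.4/74.8 = 63%.

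**3. How far the 63% depends on assumptions.** If non-relapsers start another antipsychotic at a fraction k of the relapsers' rate, each arm's starters are proportional to P + k(1 − P), where P is its relapse probability.

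| Assumption | Placebo share of starters |
|---|---|
| Planned effect, relapsers only (k = 0) | 63% |
| Planned effect, k = 0.25 | 57% |
| Planned effect, k = 0.50 | 54% |
| Planned effect, k = 1 | 50% |
| True HR 0.6, relapsers only | 59% |
| True HR 0.8, relapsers only | 54% |
| True HR 1.0, relapsers only | 50% |

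**4. Follow-up time.** Mean time on treatment = 26 × (1 − exp(−(λ + δ)))/(λ + δ): placebo 15.1 weeks, pimavanserin 18.5 weeks. Thirty days is 4.29 weeks, so the time over which events are attributed averages 19.4 and 22.8 weeks. The post-relapse part is 0.533 × 4.29/19.4 = 11.8% on placebo and 0.307 × 4.29/22.8 = 5.8% on pimavanserin.

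**5. Illustration in percentage points (both rates assumed).** Let f be the fraction of relapsers who start another antipsychotic in the window, and q the fraction of those with an event due to it. The excess on placebo is (53.3% − 30.7%) × f × q, or 22.5 points × f × q before rounding: 0.6 points at f = 0.25, q = 0.10; 2.3 at f = 0.50, q = 0.20; 6.8 at f = 1, q = 0.30. The documents give neither f nor q.

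**The case against.** Several points against a stronger reading stand.

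- **Direction.** A reader might infer that rescue harms fall mostly on placebo and make pimavanserin look safer than it is. The documents do not establish this. It needs the planned effect and use mainly by relapsers. The SAP reports counts and percentages of subjects, not rates per person-time, and pimavanserin subjects have about 18% more attributed time (22.8/19.4 = 1.18), which pushes crude percentages the other way.
- **Cause.** The medication table does not allocate adverse events. Any imbalance would come from unequal relapse combined with the 30-day window; the table only leaves it unseen.
- **Open-label period.** A reader might suspect the same gap for open-label non-responders. The not-randomized column already shows their medications and their events.
- **Mortality.** Protocol 1.3.1 notes that "elderly patients with dementia-related psychosis treated with antipsychotic drugs are at an increased risk of death". This is a class warning in pimavanserin's own labelling. It does not show that other antipsychotics carry more risk than pimavanserin.
- **Timing of rescue.** Treatment with another antipsychotic is itself a relapse criterion, and SAP 13.1 tabulates that criterion by arm. Antipsychotics started by the last dose appear under SAP 10.2.2. The share started only afterwards is unknown.
- **Other sources.** Listings are sorted by randomized group (SAP 5.1) and adverse event listings carry onset dates and required therapy (SAP 14.1), so use by arm could be reconstructed by hand. Table specifications are in a separate document that was not available.
- **The window.** Thirty days matches adverse event collection in Protocol 7.1.1 and is a legitimate choice.

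These points limit the claim about bias. They do not supply a by-arm summary of post-treatment medication or relate event onset to its start.

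**Conclusion.** The gap in the planned tables is real. Double-blind adverse events are attributed by arm for 30 days past the last dose, while drugs started in that period are summarized without regard to arm. If the planned effect holds and rescue goes only to relapsers, about 63% of the rescue exposure would be on placebo (47.4 of 74.8 relapses); with no effect or equal use in all subjects it is 50%. Neither the size nor the net direction of any distortion can be determined, because rescue use and resulting event rates are not given. This is a worthwhile, inexpensive improvement in transparency. No design figure changes, and the 30-day table need not be replaced.

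**What to change.** 1. **SAP 10.3:** also summarize post-treatment medications for the Double-blind Safety Analysis Set by treatment group, with non-study antipsychotics identifiable.
2. **SAP 14.1:** keep the 30-day table as primary. Add a supplementary by-arm display of double-blind treatment-emergent, serious and fatal events, split by onset: up to the last dose; after the last dose but before any non-study antipsychotic; and after such a drug is started.
3. **Protocol 4.5 and 6.3.8:** reconcile the two so that medications are clearly recorded through the follow-up call, including after early termination.

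The cost is a few tables from data that Protocol 6.3.8 and Table S-2 already schedule, and one sentence in Protocol 4.5. The downside is that the split in item 2 depends on outcome: it moves more follow-up out of the on-treatment category in the arm with more relapses. It should be labelled descriptive.

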11 EXTENT OF EXPOSURE AND TREATMENT COMPLIANCE

11.1 Exposure to Study Drug

The duration of exposure during the open-label period and the double-blind period for a given subject will be calculated separately. Duration of exposure to study drug will be summarized descriptively as both continuous and categorical variables for the open-label period and the double-blind period.

11.1.1 Analysis for the Open-label Period

Duration of exposure during the open-label period for a given subject is calculated as follows:

$$\text{OL Duration of exposure} = \text{last OL dose date} - \text{first OL dose date} + 1.$$

For the categorical presentation of duration of exposure during the open-label period, the number and percentage of subjects in each of the following categories will be displayed: <1 week, 1 to <2 weeks, 2 to <4 weeks, 4 to <8 weeks, 8 to <12 weeks, and ≥ 12 weeks. Summaries of duration of exposure will be provided for the Open-label Safety Analysis Set. Kaplan-Meier curves of duration of exposure will also be provided.

11.1.2 Analysis for the Double-blind Period

Duration of exposure during the double-blind period for a given subject is calculated as follows:

$$\text{DB Duration of exposure} = \text{last DB dose date} - \text{first DB dose date} + 1$$

For the categorical presentation of duration of exposure during the double-blind period, the number and percentage of subjects in each of the following categories will be displayed: <1 week, 1 to <2 weeks, 2 to <4 weeks, 4 to <8 weeks, 8 to <12 weeks, 12 to <18 weeks, 18 to <26 weeks, and ≥ 26 weeks. Summaries of duration of exposure will be provided for the Double-blind Safety Analysis Set. In addition, Kaplan-Meier curves of duration of exposure will be provided.

11.2 Study Drug Compliance

Study drug dosing compliance (in percentage) for the open-label period and the double-blind period for a given subject will be calculated separately. Study drug compliance will be summarized descriptively as both continuous and categorical variables for the open-label period and the double-blind period. For the categorical presentation, the number and percentage of subjects in each of the following categories will be presented: <80%, 80 to 120%, and >120%.

11.2.1 Analysis for the Open-label Period

Study drug compliance during the open-label (OL) period for a given subject is calculated as follows:

$$\text{Compliance} = \left[\frac{\text{OL tablets dispensed} - \text{OL tablets returned}}{2 \times \text{OL duration of exposure}} \right] \times 100\%$$

Summaries of compliance will be provided for the Open-label Safety Analysis Set.

11.2.2 Analysis for the Double-blind Period

Study drug compliance (in percentage) during the double-blind (DB) period for a given subject is calculated as follows:

$$\text{Compliance} = \left[\frac{\text{DB tablets dispensed} - \text{DB tablets returned}}{2 \times \text{DB duration of exposure}} \right] \times 100\%$$

Summaries of compliance will be provided for the Double-blind Safety Analysis Set.

12 EFFICACY ANALYSES

Efficacy analyses of the primary and key secondary endpoints for the double-blind period will be performed on the ITT Analysis Set and the Per-protocol Analysis Set. Efficacy analyses of the exploratory efficacy endpoints for double-blind period will be performed on the ITT Analysis Set. The following summaries will be provided:

1. by treatment group (placebo and pimavanserin);
2. by dose level (20 and 34 mg) of double-blind pimavanserin administered during the double-blind period for the pimavanserin group. No formal comparisons between the dose levels (20 and 34 mg) will be performed.

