5 INVESTIGATIONAL PRODUCT

5.1 Investigational Product Description

The investigational product will be pimavanserin 34 mg (provided as 2×17 mg tablets), pimavanserin 20 mg (provided as 2×10 mg tablets), and matching placebo (2×placebo tablets). Placebo tablets will be size- and color-matched to the pimavanserin tablets corresponding to the subject's dose level at the end of the open-label period. Tablets will be administered orally as a single dose once daily (QD).

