5.1.4 Dose Adjustments/Modifications/Delays

The first dose of open-label pimavanserin 34 mg will be taken at the beginning of the open-label period (Week 0 [Visit 2]). Pimavanserin will continue daily at this dose level for at least the first week of treatment. After the first week, if the subject is unable to tolerate the 34 mg dose, the dose may be decreased to 20 mg at any study visit (scheduled or unscheduled) until Week 4 (Visit 4). If the dose is decreased to 20 mg it may later be increased to 34 mg based on investigator judgment at any study visit (scheduled or unscheduled) until Week 4 (Visit 4). After Week 4 (Visit 4), the dose of study drug will remain fixed at either 34 mg or 20 mg once daily.

When the dose is adjusted, subjects should be instructed to return all treatment kits, blister cards, and unused tablets from the previous dose level before the next dose level is dispensed. Dose adjustments will be recorded in the interactive response technology (IRT) system.

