13.3 Exploratory Efficacy Analysis

13.3.1 Analysis for the Double-blind Period

Exploratory efficacy variables SAPS-H+D, SAPS Hallucinations domain, SAPS Delusions domain, CGI-S, ZBI, KSS, EQ-5D VAS, and EQ-5D-5L descriptive system evaluated in the double-blind period will be analyzed for the ITT Analysis Set. For each exploratory efficacy variable other than the EQ-5D-5L descriptive system, observed and change from double-blind Baseline values at each analysis visit will be summarized using descriptive statistics by treatment group (placebo and pimavanserin). In addition, the descriptive summaries will be provided by pimavanserin dose level (20 and 34 mg) for the double-blind pimavanserin group.

For each exploratory efficacy variable other than the EQ-5D-5L descriptive system, treatment comparisons will be made between the placebo group and the pimavanserin group (20 mg and 34 mg combined) using a MMRM and an ANCOVA. No adjustment for multiple comparisons will be made among the exploratory efficacy variables. At each post-baseline analysis visit, LS means and standard errors (SE), the corresponding 95% confidence interval and p-value will be presented. In addition, plots of LS mean \pm SE versus analysis visit will be provided.

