14 SAFETY ANALYSES

The safety endpoints for this study are as follows:

- Treatment-emergent adverse events (TEAEs)
- Serious adverse events (SAEs)
- Withdrawals due to adverse events (AEs)
- Potentially clinically important changes in other safety assessments
- Global Clinician Assessment of Suicidality (GCAS) score

- Mini-Mental State Examination (MMSE) score
- Extrapyramidal Symptom Rating Scale A (ESRS-A) score

For the open-label period, safety data will be summarized for the Open-label Safety Analysis Set. The following summaries will be provided:

1. all subjects combined;
2. by randomization status (not randomized and randomized);
3. by final dose level (20 and 34 mg) of open-label pimavanserin administered during the open-label period.

For the double-blind period, safety data will be summarized for the Double-blind Safety Analysis Set. The following summaries will be provided:

1. by treatment group (placebo and pimavanserin)
2. by dose level (20 and 34 mg) of pimavanserin administered during the double-blind period for the pimavanserin group.

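### Double-blind by-dose summaries split only the pimavanserin arm, leaving placebo undivided although each placebo subject has a dose level set before randomization

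*SAP*

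**What the plan says.** SAP 12 lists two sets of double-blind efficacy summaries. One is by treatment group. The other is "by dose level (20 and 34 mg) of double-blind pimavanserin administered during the double-blind period for the pimavanserin group". SAP 5.1.2 makes the same pair the default for the double-blind period. SAP 13.3.1 repeats it for the exploratory endpoints: "the descriptive summaries will be provided by pimavanserin dose level (20 and 34 mg) for the double-blind pimavanserin group". SAP 14 repeats it for safety: "by dose level (20 and 34 mg) of pimavanserin administered during the double-blind period for the pimavanserin group". No double-blind summary divides placebo by dose level, and dose level is not among the subgroups in SAP 12.5.1.

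On inference, SAP 12 adds: "No formal comparisons between the dose levels (20 and 34 mg) will be performed". It gives no advice on reading a dose column against placebo.

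Placebo subjects do have a dose level. Protocol 5.1 says placebo tablets are "size- and color-matched to the pimavanserin tablets corresponding to the subject's dose level at the end of the open-label period". Protocol 5.1.5 randomizes 1:1, at Week 12, between staying on the current dose and placebo matched to it. Under Protocol 5.1.4 everyone starts on 34 mg and, after the first week, "if the subject is unable to tolerate the 34 mg dose, the dose may be decreased to 20 mg". The dose can return to 34 mg on the investigator's judgment until Week 4 and is fixed after that.

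**The concern.** The two dose groups are not randomized groups. A subject is on 20 mg at Week 12 because 34 mg was not tolerated and the dose was not raised again by Week 4. Such subjects may have a different risk of adverse events, discontinuation or relapse whichever treatment they then receive.

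If a dose column is read against the whole placebo group, that difference is mixed with the treatment effect. The 20 mg column is the more exposed of the two if, as the starting dose makes likely but the documents do not state, it is the smaller group. Safety is where the reading is most natural, since an obvious question is how adverse events on 20 mg compare with placebo. The design already contains a like-for-like control for each dose, and the planned summaries do not show it.

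**Working it through.** **Does a same-dose placebo group exist?**

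| Step | Source | What follows |
|---|---|---|
| Dose fixed after Week 4 | Protocol 5.1.4 | Known before randomization |
| Randomization at Week 12, 1:1, current dose or matched placebo | Protocol 3.4, 5.1.5 | Both arms exist within each dose level |
| Placebo tablets matched to final open-label dose | Protocol 5.1 | Each placebo subject can be classified as 20 or 34 mg |
| Dose changes recorded in the IRT; open-label tables grouped by final dose | Protocol 5.1.4; SAP 5.1.1 | The variable is already in the data |
| Strata are dementia subtype and region | SAP 3.2 | Within-dose comparison is randomized, but balance within dose is not protected |

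So a randomized comparison within each dose level is available. The summary rule in SAP 5.1.2, 12 and 14 classifies by the pimavanserin dose taken in the double-blind period, so a placebo subject cannot enter it.

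**Arm size, reproduced.** Inputs from SAP 3.4: 26-week relapse 60% and 35%, dropout 25%, 75 events. With exponential times, P(event) = λ/(λ+δ) × [1 − exp(−26(λ+δ))].

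- Placebo: 0.916/(0.916+0.288) × (1 − 0.40×0.75) = 0.533.
- Pimavanserin: 0.431/(0.431+0.288) × (1 − 0.65×0.75) = 0.307.
- N = 75 / [(0.533+0.307)/2] = 178.6, which agrees with the SAP's 178, or 89 per arm. The hazard ratio is ln 0.65 / ln 0.40 = 0.470, also as stated.

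**Possible size (illustration; the share and prognosis of the 20 mg subjects are assumptions).** Let p be the share on 20 mg.

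- Cell size at p = 0.10-0.25: 89p = 8.9 to 22.25, so about 9-22 per arm.
- If 20 mg subjects differ by 10 points for reasons unrelated to treatment, undivided placebo differs from 20 mg placebo by (1−p)×10 points: 9.0 at p = 0.10 and 7.5 at p = 0.25.
- On the relapse scale, take a hazard ratio of 0.47 within each dose, 60% overall placebo relapse, p = 0.20 (about 18 per arm), and 1.5 times the relapse hazard in 20 mg subjects. The 34 mg placebo relapse-free proportion S solves 0.8S + 0.2S^1.5 = 0.40, so S = 0.430. Results, computed from unrounded values:

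| Dose | Pimavanserin relapse | Same-dose placebo | Difference, same-dose | Difference, undivided placebo (60%) |
|---|---|---|---|---|
| 20 mg | 44.9% | 71.8% | 27.0 points | 15.1 points |
| 34 mg | 32.8% | 57.0% | 24.3 points | 27.2 points |

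Over p = 5-30% and a hazard factor of 0.67-2, the 20 mg difference runs from 21.0 to 27.1 points against same-dose placebo and from 3.5 to 34.5 against undivided placebo. The error can go either way. At a hazard factor of 1 it is zero.

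**Precision lost by splitting placebo.** Use 60% and 35% with binomial standard errors, ignoring censoring.

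- 9 per arm, same-dose: √(0.24/9 + 0.2275/9) = 23 points. Undivided: √(0.24/89 + 0.2275/9) = 17 points; with a 9-point bias, root-mean-square error √(16.7² + 9²) = 19 points.
- 22 per arm, same-dose: √(0.4675/22) = 15 points. Undivided: √(0.24/89 + 0.2275/22) = 11 points; with a 7.5-point bias, √(11.4² + 7.5²) = 14 points.

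Under these assumptions the same-dose contrast removes the bias but has a slightly larger total error at 20 mg.

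**The case against.** The strongest reply is that nothing planned is wrong. A reader might infer that the SAP sets up a confounded comparison of 20 mg with placebo. It does not. Every specified treatment comparison combines the doses: the primary analysis (SAP 13.1), the exploratory models (SAP 13.3.1) and MMSE (SAP 14.7.2). The by-dose output is descriptive, and formal comparison of the two doses is excluded. Table specifications are in a separate document (SAP 1), so it cannot be seen whether a placebo column stands beside the dose columns. All of this stands, and it limits the point to how supportive tables may be read.

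A reader might also infer that placebo subjects mostly came from 34 mg, or that 20 mg subjects are frailer. The starting dose and the tolerability rule make the first likely, but the documents state neither. The 7.5-9 point figure is therefore an assumed gap scaled by an assumed share, not an estimate.

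Finally, the repair gives small cells. Same-dose placebo is a fair control in expectation only, and the precision figures show that it need not give a closer estimate at 20 mg. That also stands. It is a reason to keep the overall placebo column and to warn about imprecision. It is not a reason to omit the control that the design provides.

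**Conclusion.** The point holds as an optional, low-cost improvement to descriptive tables. The by-dose summaries cover one arm only, while the matching placebo groups exist by design, are defined before randomization and can be identified in the data. Because reduction to 20 mg depends on tolerability, a dose column read against undivided placebo may be confounded, by an amount and in a direction that the documents do not allow anyone to state. The primary analysis, the key secondary analysis, the 75 events, the 178 subjects and the stopping boundaries are unaffected. The conclusion rests on the SAP text, since the table layouts are not available.

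**What to change.** Amend SAP 5.1.2, 12, 13.3.1 and 14 so that the double-blind by-dose efficacy and safety summaries show placebo by final open-label dose level (20 and 34 mg) beside pimavanserin at the same dose. Keep the overall placebo column and keep the tables descriptive, with no added tests. Footnote each table to say that dose level was not a stratification factor and that the 20 mg cells may be small and imprecise.

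The cost is two placebo columns per by-dose table, built from a variable already recorded. No new data are needed, and there is no effect on alpha, sample size or subject management. Specifying the split before unblinding avoids a post hoc choice. The price is that the 20 mg placebo column may rest on very few subjects, which the footnote should make plain.
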